## **III. Subject Selection**

Inclusion criteria: Participants will be routine colonoscopy patients ages 18 years and over who have had a prior colonoscopy. Subjects of any race and gender will be recruited.

Exclusion criteria: Patients who are scheduled for monitored anesthesia care or general anesthesia will be excluded. Children (under 18 years) will be excluded because pediatric endoscopy patients receive general anesthesia at Massachusetts General Hospital.

First-time colonoscopy patients are excluded from the population to avoid the additional anxiety often experienced by patients undergoing this procedure for the first time. Virtual reality distraction depends largely upon the user allowing him/herself to turn attention to the virtual experiences and away from real experiences. Stressful situations, such as being in an unfamiliar medical environment awaiting an invasive procedure, activate the sympathetic nervous system. Sympathetic activation leads to hypervigilance – an active opponent of any distraction method. This pilot study will allow us to assess the effectiveness of this virtual reality pain management strategy in subjects who may not be as anxious, and allow us to determine whether the distraction method may be strong enough to reasonably offer it to first-time colonoscopy patients in future research.

All participants must be willing and able to provide written informed consent.

## **IV. Subject Enrollment**

Adult patients (over the age of 18) who have a scheduled screening or surveillance colonoscopy and have undergone at least one prior colonoscopy will be eligible for recruitment. The electronic medical record of the potential subject may be reviewed prior to contacting the patient to confirm eligibility status. Once a potential subject is identified, the patient will be sent a mailing which will outline the study, and request the opportunity for the research coordinator to contact them by phone regarding the study. This letter will provide the phone number of the research coordinator, and patients will be asked to contact the coordinator if they wish to participate. If the patient has not contacted the research coordinator two weeks after the letter has been sent, the coordinator will contact potential subjects by phone. A disclaimer on the letter will be included stating this. If the subject declines to take part in the

study, his/her name will be removed from the mailing list and they will not be contacted again regarding this research.

**Recruitment group:** Patient contacts research coordinator regarding study via phone

If the patient calls the research coordinator after receiving the letter in the mail, the coordinator will explain the study using a call script.

**Recruitment group:** Patient does not contact research coordinator after letter has been sent

If the patient does not contact the research coordinator following the mailing, the coordinator will contact him/her by telephone to explain the study using the call script and answer any questions. One phone call attempt will be made; if there is no response, the patient will not be contacted further.

All participants will be required to sign the written informed consent form on the day of the procedure.

The consent form will be pre-mailed to participants at their request.

**Patient recruitment targets:** This is a pilot study meant to assess effectiveness of a virtual reality approach to pain management. We aim to recruit 25 participants that are coming for routine screening or surveillance colonoscopies at MGH.

## V. Study Procedures

Researchers will collect data from the electronic medical records of patients on relevant medical history that might affect the colonoscopy, such as history of prior abdominal surgery, infection, or peritonitis.

If the patient agrees to participate prior to the procedure, the research coordinator will meet the subject at his/her colonoscopy appointment. The research coordinator will review the study procedures, answer any remaining questions, and obtain written informed consent using the written informed consent form. The subject will then be prepped for his/her colonoscopy by a registered nurse, and standard colonoscopy consent including consent to pharmacological sedation will be obtained by the endoscopist.

Once inside the procedure room, the research coordinator will fit the consented participant with a virtual reality head-mounted display (HMD), and set up virtual experiences for the patient to go through during their procedure through a control tablet. The HMD will completely obscure the patient's sight of the real room. The virtual environment will be enhanced with sound effects from the HMD, but the participant will still be able to hear the sounds of the procedure room so that they may respond to the verbal requests of their clinicians. The colonoscopy will proceed according to standard practice using virtual reality instead of chemical analgesics for as long as the participant chooses.

Should a participant who consented to drug administration prior to the procedure request pain medication, the research coordinator will remove the HMD and a registered nurse will administer the appropriate medications, following the standard of care at MGH.

All subjects will be asked to complete a questionnaire about their experience regardless of whether pain medication was requested. The questionnaire will collect subjective data on patient experience. The research coordinator will complete a case report form with objective data about the procedure, including duration of colonoscopy, total time spent without sedation, and events and complications during the procedure as noted by the physician. Finally, the endoscopist will also complete a brief questionnaire about his/her experience working with the patient using virtual reality distraction.

The HMD will be cleaned in between each use. A Hyperkin sanitary mask will cover all parts of the HMD that contact the user. This mask will be removed, discarded, and replaced with a new one in between each use. The entire HMD will also be wiped with a sanitary wipe before and after every use.

**Remuneration:** Participants will receive a free 4-hour parking pass at Massachusetts General Hospital for participating in this study. Otherwise, expenses will be incurred by the study subject and/or his/her insurance carrier as usual for the scheduled screening or surveillance colonoscopy.

**Costs:** Subjects will not be charged for any examination or procedure done solely for the purposes of this study. Subjects and/or their insurers will be responsible for procedures and tests performed as a part of routine clinical care.

All virtual reality hardware and software will be provided by Rendeever, Inc. They are donating their equipment to us free-of-charge for the purposes of this study. A zero-dollar purchase order and gift agreement are attached to the IRB application with details of this donation.

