## **II. Specific Aims**

The goal of this pilot study is to assess whether a virtual reality strategy is an acceptable alternative to pharmacological sedation during colonoscopy. We will collect data on patient willingness, tolerability, experience, and desire to use virtual reality during subsequent colonoscopy to draw a conclusion and make decisions about future research in this field.

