## **VI. Risks and Discomforts**

It is unknown the extent to which virtual reality may ease pain and discomfort during colonoscopy. It is possible that the virtual reality technology used in this study will not sufficiently reduce pain and discomfort. If a subject experiences a level of pain or discomfort s/he would like pain medication for, s/he has only to verbalize the request for pain medication and it will be administered. This could result in the first part of the colonoscopy being more uncomfortable than it might have been, had the subject not participated in the study.

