## **VII. Potential Benefits**

Subjects may or may not benefit from participating in this study. Should a subject complete his/her colonoscopy without pain medication, possible benefits may include shorter recovery time and lack of impairment for the rest of the day.

The results of this research will help us understand alternative methods of managing pain without the use of opioids.

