## VIII. Monitoring and Quality Assurance

Questionnaires will be entered into a password-protected RedCap database – an online data capture system approved by the Partners Human Research Committee. Hard copies of the questionnaires will be held at MGH in a designated locked cabinet to which only study staff will have access. All data will be reviewed and updated weekly by the research coordinator, and any issues will be reported to the principal investigator and dealt with accordingly. The PI will supervise data and safety monitoring at all levels, and determine when the research must be altered or stopped.

Adverse events will be reported to the IRB as outlined in Partners Adverse Event Reporting Guidelines. Adverse events will also be reported to the HRC and comply with the Partners investigator guidelines for adverse events reporting. Adverse events will be reviewed on an ongoing basis by the principal investigator. In addition to being reported to the IRB as previously noted, adverse events occurring during any colonoscopy, whether done for clinical or study purposes, will continue to be reported to the MGH GI Unit adverse event reporting system.

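### No document specifies asking participants about headset symptoms or recording events in recovery, and the SAP has no safety summary, so headset effects may be under-counted although tolerability is a stated aim.

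*Protocol*

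**What the plan says.** Protocol Section II makes tolerability an aim: "We will collect data on patient willingness, tolerability, experience, and desire to use virtual reality during subsequent colonoscopy". SAP Section 3 repeats it.

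Protocol Section V describes the intervention: "The HMD will completely obscure the patient's sight of the real room". It then has the research coordinator complete a case report form that includes "events and complications during the procedure as noted by the physician". Of the participant questionnaire it says "The questionnaire will collect subjective data on patient experience", and it is given to everyone, rescued or not. The items are not listed.

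Protocol Section VI names one risk of the intervention: "It is possible that the virtual reality technology used in this study will not sufficiently reduce pain and discomfort". No effect of wearing the headset is mentioned.

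Protocol Section VIII sends adverse events to the IRB and the HRC, with ongoing review by the principal investigator. It also sends "adverse events occurring during any colonoscopy, whether done for clinical or study purposes" to the GI Unit system.

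The SAP lists two primary and five secondary outcomes (Sections 4.1 to 4.7). The participant-rated ones are pain and discomfort, satisfaction, and willingness to repeat (4.3 to 4.5), all taken immediately after the colonoscopy. Section 6 contains no summary of adverse events.

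**The concern.** The stated capture rule has one source, the physician, and one window, the procedure. The intervention is a headset that shuts out the room. Symptoms such as nausea, dizziness or disorientation (my examples; the documents name none) would be felt by the wearer, might outlast the headset, and need not be visible to an endoscopist who is working the scope. A symptom that the participant is not asked about, or that starts in recovery, falls outside the stated rule unless someone volunteers it.

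Protocol Section II says that the pilot will inform decisions about future research, and Section III mentions offering VR to first-time patients. If the form shows few or no events, a reader could not tell whether the headset was well tolerated or whether nobody asked.

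**Working it through.** The plan gives no safety figure to reproduce, so the check is to set each possible capture route beside what it specifies.

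1. **Case report form (protocol V).** Source: physician. Window: the procedure. It does not specify participant-reported symptoms or recovery.
2. **IRB and HRC reporting (protocol VIII).** No source or window limit is stated. It refers to institutional guidelines for reporting. No elicitation method is given, so on the text alone the route carries events that have already come to notice.
3. **GI Unit system (protocol VIII).** Limited to events during a colonoscopy.
4. **Participant questionnaire (protocol V; SAP 4.3 to 4.5).** Source: participant. Timing: immediately after the colonoscopy. The items that the SAP uses are pain and discomfort, satisfaction, and willingness. None names a symptom or its cause.
5. **Completion on VR without rescue (SAP 4.1).** Rescue follows a request for pain medication. A participant who is dizzy but not in pain could finish on VR and count as a success.

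Routes 1 and 3 stop at the end of the procedure. Route 2 is open-ended but does not say how events are found. Routes 4 and 5 respond to poor tolerability without showing what caused it: a discomfort score of 7 reads the same whether it came from the headset or from the scope.

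On the analysis side, SAP Section 5 already defines a suitable denominator, all who start with VR, but Section 6 attaches no event count to it.

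One piece of arithmetic shows what a recorded zero could mean at best. If no participant out of n has an event and every event would have been found, the upper limit of the exact two-sided 95% interval is 1 − 0.025^(1/n):

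- n = 25 (target in protocol Section IV): 1 − 0.025^(1/25) = 13.7%
- n = 30 (target in SAP Section 2): 1 − 0.025^(1/30) = 11.6%

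These limits apply to the rate of events as ascertained. If capture is incomplete, a zero says less about the true symptom rate, and by how much depends on a capture share that the documents do not give.

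**The case against.** The strongest reply is that the plan has more routes than the case report form. A reader might infer that safety data are confined to what the physician notes, that headset effects will go uncollected, and that tolerability will therefore look better than it is. The documents do not support any of these.

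- The IRB and HRC route carries no in-procedure limit, and the institutional guidelines, which are not in the documents, may define events and windows.
- The questionnaire is not reproduced and may already ask about symptoms. The SAP outcome list is not an inventory of what is collected: procedure duration and time without sedation are recorded but are not SAP outcomes. The list of form contents in Section V is itself only illustrative.
- Discomfort, satisfaction and willingness are rated by participants. Because VR continues only while the participant wishes, a headset bad enough to be abandoned should lower the first primary outcome.
- Nothing ties the principal investigator's decision to alter or stop the study to physician-noted events alone. Section VIII has all data reviewed weekly.
- The recovery statement in protocol Section VII, "possible benefits may include shorter recovery time and lack of impairment for the rest of the day", is offered as a possibility and is not a study claim or endpoint.

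All of this stands, and it limits the point to under-specified collection that may under-count. It does not remove the point. No route is said to elicit symptoms, none is said to run through recovery, and any symptom items the questionnaire may hold have no planned analysis.

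It can also be said that a single-arm descriptive pilot of 25 or 30 people needs no more than this. However, tolerability is one of the few things that such a study sets out to learn.

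**Conclusion.** The point holds as a gap in ascertainment and reporting. The one stated capture rule would tend to miss symptoms that only the participant feels or that arise in recovery. The other routes either do not say how events are found or measure tolerability only indirectly, and the SAP plans no safety summary.

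The likely direction is under-counting of headset effects. The size is unknown: it depends on the true symptom rate and on the share that reaches the record, and the documents give neither. That such symptoms occur at all with this headset is an assumption; the fix would let the study find out. The conclusion also assumes that the unseen questionnaire and institutional guidelines do not already supply the symptom items and the window. If they do, what remains is to state this in the protocol and add the SAP summary.

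**What to change.** In protocol Section V:

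- Set the event window on the case report form from headset fitting to discharge from the recovery area.
- Add to the existing post-procedure participant questionnaire a short fixed list of headset symptoms (yes or no, severity, resolved or not), unless it already has one. Enter on the case report form any event that arises after the questionnaire and before discharge.
- Record whether each event began on VR, after rescue medication, or after the procedure.

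In the SAP, add a descriptive safety summary: the number of participants with any such event out of all who started on VR (the Section 5 population), with an exact confidence interval.

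The cost is a small amendment, a slightly longer questionnaire and form, some coordinator time to carry the window to discharge, and more minor events to review. No extra visit is needed, and no rule of clinical care changes.

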## **VI. Risks and Discomforts**

It is unknown the extent to which virtual reality may ease pain and discomfort during colonoscopy. It is possible that the virtual reality technology used in this study will not sufficiently reduce pain and discomfort. If a subject experiences a level of pain or discomfort s/he would like pain medication for, s/he has only to verbalize the request for pain medication and it will be administered. This could result in the first part of the colonoscopy being more uncomfortable than it might have been, had the subject not participated in the study.

## **VII. Potential Benefits**

Subjects may or may not benefit from participating in this study. Should a subject complete his/her colonoscopy without pain medication, possible benefits may include shorter recovery time and lack of impairment for the rest of the day.

The results of this research will help us understand alternative methods of managing pain without the use of opioids.

## VIII. Monitoring and Quality Assurance

Questionnaires will be entered into a password-protected RedCap database – an online data capture system approved by the Partners Human Research Committee. Hard copies of the questionnaires will be held at MGH in a designated locked cabinet to which only study staff will have access. All data will be reviewed and updated weekly by the research coordinator, and any issues will be reported to the principal investigator and dealt with accordingly. The PI will supervise data and safety monitoring at all levels, and determine when the research must be altered or stopped.

Adverse events will be reported to the IRB as outlined in Partners Adverse Event Reporting Guidelines. Adverse events will also be reported to the HRC and comply with the Partners investigator guidelines for adverse events reporting. Adverse events will be reviewed on an ongoing basis by the principal investigator. In addition to being reported to the IRB as previously noted, adverse events occurring during any colonoscopy, whether done for clinical or study purposes, will continue to be reported to the MGH GI Unit adverse event reporting system.

Statistical Analysis Plan

Virtual Reality Alternative to Pharmacological Sedation During Colonoscopy

Principal Investigator

[name]

Director, High-Risk GI Cancer Clinic

Massachusetts General Hospital

Boston, Massachusetts

Protocol Identification Number

2018P001618

ClinicalTrials.gov identifier

[figure not shown]
NCT04349150

Statistical Analysis Plan

Virtual Reality Alternative to Pharmacological Sedation During Colonoscopy

Signature Page

Principal Investigator

[name]

9-22-2021

Date

1. Introduction

Virtual reality (VR) technology has been previously explored to reduce pain perception during medical procedures through distraction. We sought to determine whether VR technology may be a feasible alternative to pharmacological sedation during colonoscopy procedures.

2. Study design

Individuals 18 years or older who are scheduled for a routine colonoscopy and who have had a prior colonoscopy will be recruited to participate. The recruitment goal for this pilot study is 30 participants. Study participants will prep for the colonoscopy according to standard practice and will be prepared for the colonoscopy according to the standard of care at Massachusetts General Hospital. All participants will undergo a VR experience through a head-mounted display (HMD) throughout the duration of the colonoscopy and the procedure will be initiated without the administration of IV sedatives or narcotics. However, standard pain medication will be available upon participant request.

All participants will be asked to complete a questionnaire about their experience. The endoscopist will also complete a questionnaire about their experience working with the participant using VR distraction.

3. Aims and objectives

The goal of the study is to assess whether VR is an acceptable alternative to using pharmacological sedation during colonoscopy procedures. Data will be collected on participant willingness, tolerability, experience, and desire to use VR during subsequent colonoscopies.

4. Outcomes

4.1 Primary Outcome 1: Proportion of Individuals Who Complete Colonoscopy Using Virtual Reality and no Pharmacological Rescue

This outcome will be measured as x/n , where x = number of participants who completed colonoscopy using virtual reality and no pharmacological rescue, and n = total number of participants who initiated colonoscopy using virtual reality. This data will be collected immediately following the colonoscopy.

4.2 Primary Outcome 2: Cecal Intubation Rate

This outcome will be defined as the cecal intubation rate of colonoscopies performed on participants using VR and no pharmacological sedation. It will be measured as x/n , where x = number of subjects in whom cecal intubation is achieved when subject is using virtual reality and no pharmacological sedation, and n = total number of participants who initiated colonoscopy using virtual reality. This data will be collected during the colonoscopy.

4.3 Secondary Outcome 1: Participant-reported Pain and Discomfort Levels

Participants will rate their pain and discomfort on a numeric rating scale of 1-10 (1 = no pain/discomfort, 10 = extreme pain/discomfort). This data will be collected immediately following the colonoscopy.

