4.4 Secondary Outcome 2: Participant Satisfaction

Participants will rate their satisfaction with their experience using virtual reality during colonoscopy on a numeric rating scale of 1-10 (1 = not satisfied, 10 = extremely satisfied). This data will be collected immediately following the colonoscopy.

4.5 Secondary Outcome 3: Participant Willingness to Undergo Future Colonoscopies With Virtual Reality and no Pharmacological Sedation

Participants will rate their willingness to undergo future colonoscopies using virtual reality and no-pharmacological sedation as "Yes," "Maybe," or "No." This data will be collected immediately following the colonoscopy.

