4.6 Secondary Outcome 4: Endoscopist Satisfaction

Endoscopists will rate their satisfaction performing colonoscopy on participants using virtual reality instead of pharmacological sedation on a numeric rating scale of 1-10 (1 = not satisfied, 10 = extremely satisfied). This data will be collected immediately following the colonoscopy.

4.7 Secondary Outcome 5: Endoscopist Willingness to Incorporate Virtual Reality Into Regular Colonoscopy Practice

Endoscopists will indicate whether they would incorporate VR into their regular colonoscopy practice by selecting one of the following: "Yes" "No" or "Yes, but I would use virtual reality as an adjunct therapy rather than a standalone therapy." This data will be collected immediately following the colonoscopy.

5. Populations to be analyzed

The population analyzed will consist of all participants who initiate the study using the virtual reality technology.

6. Analyses

6.1 Primary Outcome 1: Proportion of Participants Who Complete Colonoscopy Using Virtual Reality and no Pharmacological Rescue

This outcome will be analyzed as a percent from the proportion of participants who complete colonoscopy using VR and no pharmacological rescue.

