6.3 Secondary Outcome 1: Participant-reported Pain and Discomfort Levels

The mean values for participants' pain and discomfort will be calculated, along with the standard deviation.

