6.4 Secondary Outcome 2: Participant Satisfaction

The mean values for participant satisfaction will be calculated, along with the standard deviation. Correlation between satisfaction values and values for pain and discomfort will be assessed using the Pearson r correlation.

6.5 Secondary Outcome 3: Participant Willingness to Undergo Future Colonoscopies With Virtual Reality and no Pharmacological Sedation

Counts of participants selecting “Yes,” “Maybe,” and “No” will be analyzed as percentages.

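### Rescued participants' ratings, pain above all, can mix the VR period with the medicated period and may be given soon after dosing, and the SAP pools them with no later rating and no split by rescue status

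*SAP*

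**What the plan says.** **Timing.** For pain and discomfort, SAP 4.3 states: "This data will be collected immediately following the colonoscopy". SAP 4.4 (satisfaction) and 4.5 (willingness) set the same time. On willingness, SAP 4.5 says: "Participants will rate their willingness to undergo future colonoscopies using virtual reality and no-pharmacological sedation".

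**Who rates.** Protocol section V: "All subjects will be asked to complete a questionnaire about their experience regardless of whether pain medication was requested". SAP section 5: "The population analyzed will consist of all participants who initiate the study using the virtual reality technology". Rescued participants are therefore asked for ratings and belong to the analysis population.

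**What rescue involves.** Protocol section V says that, on request, "the research coordinator will remove the HMD and a registered nurse will administer the appropriate medications". This happens during the colonoscopy, before the questionnaire.

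**After medication.** Protocol section VII says that for someone who finishes without pain medication, "possible benefits may include shorter recovery time and lack of impairment for the rest of the day".

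**Analysis.** SAP 6.3: "The mean values for participants' pain and discomfort will be calculated, along with the standard deviation". SAP 6.4 adds: "Correlation between satisfaction values and values for pain and discomfort will be assessed using the Pearson r correlation". SAP 6.5 reports willingness as percentages. None of the three sections separates rescued from unrescued participants.

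**The concern.** Tolerability, experience and desire to use VR again are stated aims (Protocol section II, SAP section 3). Rescued participants are those for whom VR alone was not enough, so their answers bear directly on acceptability. Two features make those answers hard to interpret.

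- **Period rated.** The pain item in SAP 4.3 names no period. A rescued participant may rate the time under VR, the time after medication, or a blend. Two people giving the same number may be describing different things.
- **State when rating.** A rescued participant may answer soon after receiving medication. Someone who finished on VR alone answers unmedicated.

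At stake are the pooled pain mean, the satisfaction mean, the willingness percentages and the satisfaction-pain correlation. A reader could not tell how far any of these describes VR and how far it describes VR followed by a drug.

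**Working it through.** The plan states no rescue rate, rating SD or drug effect, so there is no figure to reproduce. The check has two parts.

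**1. Setting the passages side by side**

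- Rescue is given during the procedure (Protocol V) and ratings follow immediately after it (SAP 4.3 to 4.5). A rescued participant therefore rates after dosing. The interval is unknown, because the time of rescue is not fixed and the word immediately is not defined.
- Protocol VII lists absence of impairment that day as a possible benefit of avoiding medication. This implies that medicated patients may be impaired after the procedure, which would include the time of rating.
- Neither document describes a rating before rescue, a delayed or repeated rating, a readiness check before the form, or a summary by rescue status.
- The satisfaction item (SAP 4.4) does refer to the experience of using VR. The missing rating period is therefore chiefly a problem for pain.

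**2. Illustrative size**

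Inputs from the documents: a 1-10 scale (SAP 4.3), and a planned n of 25 (Protocol IV) or 30 (SAP 2). Assumed inputs: 10-40% rescued, and an average shift of 1-3 points in a rescued participant's rating.

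Shift in pooled mean = rescued fraction × shift per rescued participant.

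| Rescued | 1 point | 2 points | 3 points |
|---|---|---|---|
| 10% | 0.1 | 0.2 | 0.3 |
| 20% | 0.2 | 0.4 | 0.6 |
| 40% | 0.4 | 0.8 | 1.2 |

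For scale, the 95% half-width of a mean is 1.96 × SD / √n. With an assumed SD of 2 to 2.5:

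- n = 30: 1.96 × 2 / √30 = 0.72, and 1.96 × 2.5 / √30 = 0.89.
- n = 25: 1.96 × 2 / √25 = 0.78, and 1.96 × 2.5 / √25 = 0.98.

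Each willingness answer that changes moves a category by 100/30 = 3.3 percentage points or 100/25 = 4.0.

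For the correlation, a small simulation used n = 30, an average undistorted r of about -0.57, and 20% rescued (the 6 participants with the highest pain). Lowering their pain by 2 points changed the average r to about -0.54. Also raising their satisfaction by 2 points changed it to about -0.40. All of these settings are assumptions.

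**The case against.** The case against acting is substantial.

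- **The two primary outcomes already capture VR failure.** SAP 4.1 and 4.2 count completion and cecal intubation without drug, and neither depends on these ratings. This stands, and it limits the point to participant-reported secondary outcomes in a single-arm pilot.
- **The whole procedure may be the intended target.** If the question is how a VR-first strategy with medication on request feels overall, lower pain after medication is part of the result and no distortion. SAP section 5 is compatible with that reading. This stands as a possibility, but SAP 4.3 does not say which target is meant, so the ambiguity remains.
- **The shift may be small beside sampling error.** At 10% rescued it is 0.1-0.3 against a half-width of 0.72-0.98, and 20% with 2 points (0.4) is also smaller. This stands for low rescue rates. At 40% with 2 or 3 points (0.8 or 1.2) the shift is comparable with or larger than the half-width.
- **Immediate rating limits recall decay.** This stands. A next-day rating adds recall error and non-response, and if the medication affected memory it would inherit that problem. Hence the later rating is proposed only as a sensitivity analysis.
- **The questionnaire is not among the documents.** It may already define the period rated. If so, only SAP 4.3 needs to say so.

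A reader might also infer that ratings are taken at the peak of drug effect. No drug, dose, time of administration or duration is given, so the text supports only that ratings may come soon after dosing. The impairment itself is inferred from a cautiously worded benefits statement that says nothing about the ability to rate pain.

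**Conclusion.** The point holds as a cheap improvement. Rescued participants' ratings, especially of pain, can mix two periods and may be given while the participant is still affected by medication. The SAP pools them without any means of seeing the effect.

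The size is unknown. The 0.1-1.2 point range rests wholly on the assumed 10-40% rescue rate and 1-3 point shift. The direction is unknown too. A reader might infer a bias in favour of VR, on the view that medication dulls pain or its memory. The documents do not establish that, and a bad start before rescue could pull ratings the other way.

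It would also be too strong to say that nothing ties the ratings to VR, since satisfaction is asked about the VR experience, or that the main conclusions fail, since both primary outcomes and the endoscopist ratings are untouched.

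**What to change.** 1. In SAP 4.3 and the questionnaire, ask participants to rate pain and discomfort for the part of the procedure done with VR before any medication. The satisfaction item already refers to the VR experience.
2. Keep the immediate rating as the main result. Have the existing research coordinator repeat the pain/discomfort, satisfaction and willingness items by telephone the next day for all participants, and report the answers as a sensitivity analysis.
3. In SAP 6.3 to 6.5, also show the ratings by rescue status. This does not separate drug effect from VR experience within the rescued group, but it shows how far the pooled figures depend on that group.

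**Cost.** A wording change, a minor amendment and 25-30 short calls. One day of recall and a few non-responders affect only the sensitivity analysis.

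**If data collection is already complete,** only item 3 and a stated limitation remain possible.
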